#### 8.3.3 Summary Statistics

Data will be summarized by means of summary statistics. Summary statistics will be provided for the variables described in the following sections.

the format YYYY-MM-DD

Categorical data will be presented as counts and percentages, i.e., n (xx.x%). Percentages will be based on the number of subjects in the analysis data set used and given as integers. Zero frequencies will be given without percentages.

For continuous variables, these statistics will include the number of subjects, mean, SD, median, minimum, and maximum.

All variables will be analyzed descriptively with appropriate statistical methods: categorical variables by frequency tables (absolute and relative frequencies) and continuous variables by sample statistics (i.e., number of observations, mean, SD, 95% CI of the mean, minimum, median, first and third quartiles and maximum). Minimum and maximum values will be displayed as reported.

Since the efficacy primary and secondary endpoints are captured at multiple visits, the method selected to analyze the endpoints which are treated as continuous will be a Mixed Model for Repeated

ANVS-22001		Version 2.1, 11 January 2024
ANNOVIS BIO, INC.	CONFIDENTIAL	Statistical Analysis Plan

Measures (MMRM) with change from Baseline score as the response (dependent variable) and with Baseline value as a covariate and treatment, timepoint, treatment-by-timepoint interaction as fixed effects (independent variables). Estimation of parameters will be done by means of Restricted Maximum Likelihood method. The Unstructured (UN) variance-covariance structure will be initially used to explore the variance-covariance matrix across visits. If the algorithm doesn't converge, a heterogeneous Toeplitz (TOEPH) as the covariance matrix will be tried first, and then first-order autoregressive (AR(1)) to achieve convergence. The Kenward-Roger approximation will be used to estimate denominator degrees of freedom. The two-sided 95% CI of the treatment differences will be presented.

The endpoints will be analyzed using the model explained above as follows:

<Endpoint>= intercept + Base + T + V + T\*V, with Base: baseline score; T: treatment; V: post-baseline visit (Month 1, Month 2, Month 3, Month 6).

Treatment comparisons (10 mg vs. Placebo / 20 mg vs. Placebo) will be carried out by means of the contrasts on the treatment factor by visit effect in SAS® Software, using proc mixed. Treatment effects will be estimated by means of Least Square Means (LSM) and 95% CI. Differences between treatments (10 mg – Placebo / 20 mg – Placebo) will be estimated and resulting 2-sided p-values and associated 95% CI will be presented.

# 8.3.4 Patient/Subject Data Listings

Data collected in the electronic case report form (eCRF) will generally be listed. eCRF check questions (e.g., reminders) will not be listed.

Listings will be sorted by treatment group, study center, patient/subject id, visit and assessment time as applicable. If center id is part of patient/subject id, then center could be omitted.

In CRF modules where a date is recorded, the relative day may be included in the corresponding listing. In modules where both a start date and stop date are recorded, the duration may be included in the listing.

#### 8.3.5 Subject Disposition

The numbers of subjects screened, enrolled, completed, discontinued, and withdrawn during the study, as well as the reasons for all post-enrolment discontinuations will be listed and/or summarized by treatment group. Disposition and reason for study discontinuation will also be provided as a by-subject listing.

#### 8.3.6 Demographic and Other Baseline Characteristics

Demographics and baseline characteristics will be summarized by treatment group using appropriate descriptive statistics.

The following summaries will be given by treatment and in total:

- Demography
  - Age (years)
  - Age (years), categories (40 to <65, 65 to <75, 75 to <85)
  - Sex (Male or Female)
  - Race (White, Asian, Black or African American, American Indian or Alaska Native, Native Hawaiian or Other Pacific Islander)
  - Ethnicity (Hispanic or Latino, Not Hispanic or Latino, Not Reported, Unknown)

- Substance use tobacco and alcohol
  - Smoker (Never, Current or Former)
  - Alcohol user (Never, Current or Former)
- Time since diagnosis of Parkinson's disease

## 8.3.7 Primary Analysis

The primary efficacy endpoint in this clinical trial is the change from baseline to Month 6 in the score for MDS-UPDRS part II (OFF-state) between each of the two regimens of buntanetap and Placebo.

The statistical hypothesis to be tested for primary efficacy is described as:

• Null Hypothesis (H0):

The difference in change in MDS-UPDRS Part II (OFF-state) scores from Baseline to Month 6, between treatment (active vs placebo) regimen = 0.

• Alternative Hypothesis (H1):

The difference in change in MDS-UPDRS Part II (OFF-state) scores from Baseline to Month 6, between treatment (active vs placebo) regimen  $\neq$  0.

The primary endpoint will be analyzed via MMRM. The model will include treatment, timepoint, treatment-by-timepoint interaction as the fixed effects and baseline as the covariate. The variance-covariance matrix will be assumed to be unstructured.

This analysis will be conducted after all subjects have reached Month 6 or early withdrawal, whichever comes first. The primary analysis will be conducted in ITT. The mITT and PPS will be used to support the primary analysis.

Descriptive statistics per visit and change from baseline for each visit will be provided.

#### 8.3.8 Secondary Analysis

Secondary efficacy endpoints in this clinical trial are

- Change from baseline to Month 6 in the sum of the score of MDS-UPDRS Parts II+III OFFstate
- Change from baseline to Month 6 in the score of MDS-UPDRS Part III OFF-state
- Change from baseline to Month 6 in the total score for MDS-UPDRS OFF-state
- Percentage of responders with "Much improved" or "Very much improved" on PGIC ONstate
- Change from baseline to Month 6 on CGIS OFF-state.

#### Change from baseline to Month 6 in the sum of MDS-UPDRS Parts II+III – OFF-state

The MDS-UPDRS is a 50-item rating scale designed to assess Parkinson's disease-related disability and impairment. The scale comprises four parts: Part I evaluates mentation, behavior, and mood symptoms; Part II evaluates ADL; Part III evaluates motor function; and Part IV evaluates complications of dopaminergic therapy. Part II contains 13 questions which are to be completed by the participant (range 0-52). Part III contains 33 scores based on 18 items (Range 0-132). MDS-UPDRS Part II and III combined score equals the sum of Parts II and III (Range 0-184). A higher score indicates more severe symptoms of PD.

MDS-UPDRS Parts II+III will be analyzed by MMRM, similar to the primary efficacy endpoint.

Change from baseline to Month 6 in the MDS-UPDRS Part III – OFF-state

Part III contains 33 scores based on 18 items (Range 0-132).

MDS-UPDRS Part III will be analyzed by MMRM, similar to the primary efficacy endpoint.

Change from baseline to Month 6 in the MDS-UPDRS Total score - OFF-state

The UPDRS is a 50-item rating scale designed to assess Parkinson's disease-related disability and impairment. The scale comprises four parts:

Part I evaluates mentation, behavior, and mood symptoms;

Part II evaluates ADL;

Part III evaluates motor function; and

Part IV evaluates complications of dopaminergic therapy.

The MDS-UPDRS Total score is the sum of the subscale scores for Parts I to III and ranges from 0 to 236, with higher scores reflecting greater severity. MDS-UPDRS will be assessed by the investigator at baseline and each visit at the clinic (Month 1, Month 2, Month 3, and Month 6).

MDS-UPDRS Total score will be analyzed by MMRM, similar to the primary efficacy endpoint.

Percentage of responders with "Much improved" or "Very much improved" on PGIC - ON-state

The PGIC is the participant-reported outcome. The qualitative assessment of meaningful change will be determined by the participant in response to the question, "Compared to your condition at the beginning of treatment, how much has your condition changed?" Scores are

1= very much improved

2= much improved

3= minimally improved

4= no change

5= minimally worse

6= much worse

7= very much worse

The assessment is done during visits at the clinic (Month 1, Month 2, Month 3, and Month 6) and ONstate i.e., subjects were allowed to treat the PD with SOC medication.

For PGIC, responders are defined as responses with score 1 (very much improved) and score 2 (much improved). PGIC will be analyzed for responders (scores 1 and 2) using logistic regression method.

Descriptive statistics for each visit will be produced for the PGIC.

Change from baseline to Month 6 on CGIS – OFF-state

The clinical global impressions scale on the severity of movement impairment as assessed by the site rater. Site raters will be asked: Considering your total clinical experience with the Parkinson disease population, how ill is the patient's movement at this time? Answers were based on a 7-point scale, with 1= not assessed, 2= very mild, 3= mild, 4= moderate, 5= moderate severe, 6= severe, 7= extremely severe.

The assessment is done at baseline visit and during visits at the clinic (Month 1, Month 2, Month 3, and Month 6) and OFF-state i.e., 12 hours after last intake of medication of standard of care for Parkinson's disease.

For CGIS, responders are defined as a decrease in CGIS score from baseline to Month 6. CGIS will be analyzed for responders using logistic regression method.

Descriptive statistics and change from baseline for each visit will be produced for the CGIS.

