The PGIC is the participant-reported outcome. The qualitative assessment of meaningful change will be determined by the participant in response to the question, "Compared to your condition at the beginning of treatment, how much has your condition changed?" Scores are: 1=very much improved; 2=much improved; 3=minimally improved; 4=no change; 5=minimally worse; 6=much worse; and 7=very much worse. Percentage of responders with much improved and very much improved on PGIC scale will be assessed. PGIC will be taken at home while the subject is during ON-state (with their SOC for Parkinson disease).

5. Change From Baseline to Month 6 on Change on Clinical Global Impression of Severity (CGIS) (OFF-state)

The Clinical Global Impressions Scale on the severity of movement impairment as assessed by the site rater. Site raters will be asked: Considering your total clinical experience with the Parkinson disease population, how ill is the patient at this time? Answers were based on a 7-point scale, with 1=not assessed, 2= very mild, 3= mild, 4= moderate, 5= moderate severe, 6= severe, 7=extremely severe.

Exploratory Endpoints:

1. Changes From Baseline to Month 6 in The Plasma Biomarker Measured

Potential biomarkers to be measured in plasma are Neurofilament Light (NFL), Glial fibrillary acidic protein (GFAP) and TDP43.

2. Change From Baseline to Month 6 in WAIS Coding Test (OFF-state)

In the digital symbol coding test individuals are asked to record associations between different symbols and numbers within time limits. The Total score is the sum of all the correctly coded numbers.

3. Change From Baseline to Month 6 in MMSE (OFF-state)

The Mini-Mental State Exam (MMSE) is a 30-point test, widely used test of cognitive function.

4. Pharmacokinetics

The following PK parameters will be determined, as data permit: Area under the curve (AUC), Cmax, Tmax, t_{1/2}, and CL.

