		The MDS-UPDRS is a 50-item rating scale designed to assess Parkinson's disease-related disability and impairment. The scale comprises four parts: Part I evaluates mentation, behavior, and mood symptoms; Part II evaluates ADL; Part III evaluates motor function; and Part IV evaluates complications of dopaminergic therapy. The Total score is the sum of the subscale scores for Parts I to III and ranges from 0 to 236, with higher scores reflecting greater severity.
	4.	Percentage of Responders with "Much Improved" or "Very Much Improved" on Participant Global Impression of Change (PGIC) (ON-state)
		The PGIC is the participant-reported outcome. The qualitative assessment of meaningful change will be determined by the participant in response to the question, "Compared to your condition at the beginning of treatment, how much has your condition changed?" Scores are: 1=very much improved; 2=much improved; 3=minimally improved; 4=no change; 5=minimally worse; 6=much worse; and 7=very much worse. Percentage of responders with much improved and very much improved on PGIC scale
		will be assessed. PGIC will be taken at home while the subject is during ON-state (with their Standard of care (SOC) for Parkinson disease).

Exploratory

Objective	Endpoint	
	
 
Change from baseline to Month 6 on Clir Global Impression of Severity (CGIS) (Of state)
 
	nical FF-
	The CGIS on the severity of movement impairment as assessed by the site rater. S raters will be asked: Considering your total experience with the Parkinson disease pop how ill is the patient's movement at this time Answers were based on a 7-point scale, wit 1=not assessed, 2= very mild, 3= mild, 4= moderate, 5= moderate severe, 6= severe	ite clinical ulation, e? h

moderate, c	– model
7=extremely	severe.

Investigate change after buntanetap in potential biomarkers and improvement	1.	Change from baseline to Month 6 in the plasma biomarkers measured
in cognitive functions		Potential biomarkers to be measured in plasma are Neurofilament Light (NFL), Glial fibrillary acidic protein (GFAP) and TAR DNA-binding protein 43 (TDP43).
	2.	Change from baseline to Month 6 in Wechsler Adult Intelligence Scale (WAIS IV) coding test (OFF-state)
		In the digital symbol coding test individuals are asked to record associations between different symbols and numbers within time limits. The Total score is the sum of all the correctly coded numbers. The higher score indicates better outcome.

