#### 8.3.2 Definitions

MMSE – OFF- state	Mini-Mental State Examination is a 30-point test, widely used test of cognitive function.
PGIC – ON-state	Participant Global Impression of Change is the participant-reported outcome.
	The qualitative assessment of meaningful change will be determined by the participant in response to the question, "Compared to your condition at the beginning of treatment, how much has your condition changed?" Scores are 1= very much improved; 2= much improved; 3= minimally improved; 4= no change; 5= minimally worse; 6= much worse; 7= very much worse
CGIS – OFF-state	Clinical Global Impression of Severity is a scale on the severity of movement impairment as assessed by the site rater. Site raters will be asked: Considering your total clinical experience with the Parkinson disease population, how ill is the patient's movement at this time? Answers were based on a 7-point scale, with 1= not assessed, 2= very mild, 3= mild, 4= moderate, 5= moderate severe, 6= severe, 7=extremely severe
WAIS-IV – OFF- state	In the digital symbol Wechsler Adult Intelligence Scales, 4th edition, coding test individuals are asked to record associations between different symbols and numbers within time limits. The Total score is the sum of all the correctly coded numbers.

MDS-UPDRS – OFF-state	Movement Disorder Society-Unified Parkinson's Disease Rating Scale is a 50-item rating scale designed to assess Parkinson's disease-related disability and impairment comprising the four parts:
	Part I - Non-Motor Aspects of Experiences of Daily Living
	Part II - Motor Aspects of Experiences of Daily Living
	Part III - Motor examination
	Part IV - Motor complications
Treatment- Emergent Adverse Event	Treatment emergent adverse events (TEAEs) are defined as undesirable events not present prior to medical treatment, or an already present event that worsens either in intensity or frequency following the treatment. If an AE starts at the same day as the study drug the start time of the AE will be compared with the start time of the administration of study drug. If the start time of the AE is at or after start time of administration of study drug the AE is a TEAE. If no clear assignment is possible due to incomplete or missing start dates, the AE will be counted as TEAE.

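### CGIS code 1 is labelled as not assessed, yet any fall in score counts as a response; the label and the responder rule must be reconciled before unblinding

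*SAP*

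**What the plan says.** Four code lists agree with one another. Protocol 2.2 has "1=not assessed, 2= very mild, 3= mild, 4= moderate". SAP 4 has "1=not assessed, 2= very mild, 3= mild, 4= moderate, 5= moderate severe, 6= severe". SAP 8.3.2 has "Answers were based on a 7-point scale, with 1= not assessed, 2= very mild, 3= mild". SAP 8.3.8 has "1= not assessed, 2= very mild, 3= mild, 4= moderate". In each, severity starts at 2 and ends at 7, and code 1 is not a severity level.

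SAP 8.3.8 then sets the rule, "For CGIS, responders are defined as a decrease in CGIS score from baseline to Month 6", and the test, "CGIS will be analyzed for responders using logistic regression method". It also asks for descriptive statistics and change from baseline at each visit. No minimum change is required and no code is excluded.

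Other provisions that bear on the test:
- SAP 8.3.1 places CGIS last of five secondary endpoints in a fixed sequence, at alpha 0.025 for each dose.
- SAP 8.3.3 gives a baseline covariate to endpoints treated as continuous, and SAP 8.7 names baseline only for the primary MMRM. Neither covers the logistic tests.
- SAP 8.9 sets an imputation rule for the primary endpoint only.

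**The concern.** The label and the rule cannot both be right. If code 1 means that no rating was made, the rule turns an absent rating into the best possible outcome for anyone rated at baseline. It also removes any chance of response from a patient coded 1 at baseline, and the descriptive change from baseline is distorted in the same way.

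At stake is the meaning of an endpoint inside the alpha-controlled sequence. If the code, the missing-data rule or the covariate is chosen after unblinding, the choice can be questioned as driven by the result. Two related gaps belong in the same edit: the logistic model names no baseline covariate although baseline CGIS is collected, and nothing says how a missing Month 6 value enters the test. The missing-value gap applies equally to PGIC, which ranks fourth and is also tested by logistic regression.

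**Working it through.** **No plan figure to reproduce.** The documents give no response rate, power or code-1 frequency for CGIS. Their power statements concern MDS-UPDRS Part II+III and Part II.

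**Step 1: apply the rule to every code pair.** Codes 1 to 7 at two visits give 7 × 7 = 49 pairs. Month 6 is below baseline in 7 × 6 / 2 = 21. Six of these (baseline 2, 3, 4, 5, 6 or 7 with Month 6 = 1) are patients rated at baseline and not assessed at Month 6. With code 1 set to missing, 6 × 5 / 2 = 15 responder pairs remain. For baseline 2, the only responder pair is (2, 1). For baseline 1 there is none.

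**Step 2: size of the effect, under assumptions.** Inputs: 174 per arm (SAP 8.10.2); two-sided alpha 0.025 (SAP 8.3.1); assumed true response p0 = 20% in both arms; assumed share f coded 1 at Month 6.
- Observed response = f + (1 − f) × p0. For f = 2%: 0.02 + 0.98 × 0.20 = 0.216. For f = 1%: 0.01 + 0.99 × 0.20 = 0.208.
- Test: z = (active − placebo) / √[2 × p̄(1 − p̄) / 174], where p̄ is the pooled proportion. Active wins if z > 2.241. The probability is summed exactly over both binomial distributions.

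| Code 1, active v placebo | Observed response | Chance of a false win for active |
|---|---|---|
| 0% v 0% | 0.200 v 0.200 | 1.25% |
| 2% v 2% | 0.216 v 0.216 | 1.24% |
| 2% v 1.5% | 0.216 v 0.212 | 1.56% |
| 2% v 1% | 0.216 v 0.208 | 1.95% |
| 2% v 0% | 0.216 v 0.200 | 3.02% |
| 1% v 2% | 0.208 v 0.216 | 0.76% |

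At 2% v 1%, true response of 10%, 30% and 40% gives 2.37%, 1.80% and 1.69%. All these figures ignore the requirement that the dose first succeed on the primary and four earlier secondary endpoints, so the chance of a false confirmatory claim is lower.

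**Step 3: value of the baseline covariate, under assumptions.** Baseline and Month 6 severity are simulated as correlated normal variables and cut into six levels (codes 2 to 7), either at equal frequency or at −2, −1, 0, 1 and 2 SD. The treatment effect is 0.30 SD, with 174 per arm, a Wald test at two-sided 0.025 and 10,000 trials per scenario. Power (equal-frequency cuts / SD cuts):

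| Correlation | Logistic, no baseline | Logistic, linear baseline |
|---|---|---|
| 0.6 | 49.7% / 52.5% | 57.3% / 59.7% |
| 0.8 | 76.8% / 77.2% | 81.4% / 81.8% |

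**Step 4: missing Month 6 values.** The schedules in Protocol Appendix 1 and SAP Appendix 1 show neither CGIS nor PGIC at the early discontinuation visit, and SAP 8.10.2 reports about 6% dropout. Missing values will therefore occur. With 6% missing in both arms and correlation 0.6, adjusted power is 54.3% / 56.1% if these patients are excluded and 51.7% / 54.0% if they count as non-responders, against 57.3% / 59.7% with complete data.

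**The case against.** **Code 1 may be a wording slip.** Protocol Appendix 2 refers to copies of the instruments, but the CGIS form is not in the text available. If it shows 1 as the lowest severity level, the rule works and no result changes. This stands, and it is why the point asks for reconciliation and does not claim that the analysis is wrong in either particular direction.

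**An unrated patient has no score, so no decrease can be computed.** That is a sensible reading, and the blinded pre-analysis review in SAP 8.2 might catch the problem. But code 1 is listed as a point on the scale, and SAP 8.2 assigns patients to analysis sets without setting any rule for codes.

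**Nothing suggests that code 1 would differ by arm.** This stands. The trial is double-blind, and early dropouts have no scheduled CGIS, so only patients who attend Month 6 but are not rated could produce the code there. One such patient among 174 on active and none on placebo gives about 1.6% at 20% response.

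**An unadjusted logistic test is valid.** True. The covariate is an improvement in power and does not correct an error; the gain depends on the assumed effect and correlation.

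**Naming and question wording are editorial.** Agreed. A responder defined by a decrease is a dichotomised change from baseline. The rater is asked "how ill is the patient at this time" in Protocol 2.2 and "how ill is the patient's movement at this time" in the SAP, but the protocol's own lead-in already refers to movement impairment. A reader might infer that two different ratings were collected; the documents do not show that.

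**Conclusion.** The conflict is real and sits in the text of both documents: one label, repeated four times, is incompatible with the responder rule. Which of the two is wrong cannot be settled without the rating form.

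A reader might infer that unrated patients will be counted as successes, or that the CGIS error rate is inflated. The documents support neither. The meaning of code 1 on the form and its frequency are unknown, equal use leaves the false-win chance unchanged (1.24% v 1.25%), and no reason for unequal use is evident. The 1.95% at 2% v 1% is an illustration, not an estimate. Because CGIS is fifth of five, a confirmatory claim is affected only for a dose that has already succeeded on everything before it.

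The change should be made because it is nearly free before unblinding and open to challenge afterwards. The covariate gain rests on an assumed 0.30 SD effect: power rises from about 50% to 57–60% at correlation 0.6 and from about 77% to 81–82% at 0.8.

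**What to change.** Before unblinding:

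1. **Check the rating form for code 1.** If it means that no rating was made, add to SAP 8.3.2 and 8.3.8: *Code 1 is treated as missing at every visit, for the responder test and for the descriptive change.* If it is a severity level, correct the anchor in Protocol 2.2 and SAP 4, 8.3.2 and 8.3.8.
2. **Keep the logistic responder test and add baseline CGIS as a linear covariate.** If code 1 becomes missing, patients rated 2 at baseline cannot respond, so baseline entered as categories would have a cell without events. Report the number of such patients per arm.
3. **State how a missing Month 6 value enters the logistic tests for CGIS and PGIC.** If patients without a score are excluded, say that this assumes missingness is unrelated to response given arm and baseline (arm alone for PGIC, which has no baseline value). That is narrower than the MMRM assumption, because the scores at Months 1 to 3 are not used. Add missing counted as non-response as a sensitivity analysis.

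Optional: name the endpoint as a responder rate, align the rater's question, and add an ordinal or score analysis as supportive.

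Cost: a few lines in each document and one model term, with no new data. The odds ratio becomes conditional on baseline CGIS. Against complete data, excluding 6% of patients costs about 3 to 4 points of power at correlation 0.6 (57.3% to 54.3%, or 59.7% to 56.1%).

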2.0 INTRODUCTION

Currently, there is no treatment available to stop or reverse the progression of Alzheimer's (AD) and Parkinson's disease (PD). Neurodegenerative diseases such as AD and PD share many common characteristics, including the central role of neurotoxic aggregating proteins in their pathogenesis. Amyloid β (A β) and tau aggregates (senile plaques and neurofibrillary tangles, respectively) have been traditionally associated with AD, while α -synuclein (α SYN) aggregates (Lewy bodies) have been associated with PD. However, it is becoming increasingly clear that all these proteins are involved in both diseases and that aggregation of one can lead to accumulation of another. Furthermore, in several studies of brains from older AD patients, a high percentage of all AD brains present mixed pathologies, such as Lewy body disease. Several clinical trials targeting just one (often A β) of the neurotoxic aggregating proteins have failed. Finally, other fragments of Amyloid β Precursor Protein (APP) have been implicated in AD pathology. Collectively, these facts point to the need for development of combination therapies that target multiple neurotoxic aggregating proteins simultaneously, if we are to have a good chance of at least halting disease progression.

Buntanetap has a unique mechanism of action, in that it inhibits the translation and, therefore, reduces the levels of several neurotoxic aggregating proteins both *in vitro* and *in vivo*, including α SYN, APP, its fragments, and tau. All three proteins have been implicated in the pathogenesis of PD. Furthermore, at older ages, there is a high incidence of PD patients with mixed pathologies, such as PD dementia. Therefore, it is reasonable to hypothesize that inhibiting expression of all three proteins should lead to a better efficacy outcome in PD patients than inhibiting just one.

α SYN, APP, and tau contribute to the progression of AD and PD in similar ways: they impair axonal transport and lower neurotransmitter and neurotrophic factor release, they cause inflammation, they form aggregates, and, finally, they lead to nerve cell death. In our *in vitro* and *in vivo* preclinical studies, buntanetap has normalized all those actions.

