#### 8 Statistical and Analytical Plans

#### 8.1 Changes to the Planned Analyses

There have been no changes in the planned analyses in the study protocol.

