#### 8.3.1 Level of Significance, Multiple Comparisons and Multiplicity

There are two active treatment groups (10 mg and 20 mg) in the study. Each of the two active treatments will be compared to the control (two hypothesis tests for the primary endpoint). The comparison of each of the two treatment groups against control for the primary endpoint will be performed using the Hochberg step up procedure, where if the largest p-value is <0.05, then the null hypothesis will be rejected for both groups. If the largest p-value is >0.05, then the critical value for the second test will be at two-sided 0.025.

To control for study-wise type 1 error rate, a fixed-sequence hierarchical testing procedure will be applied to adjust for multiplicity arising from multiple secondary endpoints. The hierarchical testing order for the secondary endpoints are:

- 1. Change from baseline to Month 6 in the sum of MDS-UPDRS Part II+III (OFF-state)
- 2. Change from baseline to Month 6 in MDS-UPDRS Part III (OFF-state)
- 3. Change from baseline to Month 6 in MDS-UPDRS Total score (OFF-state)
- 4. Percentage of Responders with "Much Improved" or "Very Much Improved" on PGIC (ON-state)
- 5. Change from baseline to Month 6 on CGIS (OFF-state)

If the primary endpoint of both dose groups are statistically significant, the secondary endpoints for each dose group will be tested in a hierarchical manner at alpha 0.025. If the primary endpoint of a specific dose group is statistically significant, the secondary endpoints for that dose group will be tested in a hierarchical manner at alpha 0.025. If the primary endpoint of both dose groups are not statistically significant, the hypothesis testing for all subsequent endpoints will be considered exploratory. Two flowcharts are also presented in the following.

All other exploratory endpoints are considered supportive and no adjustment for multiplicity will be applied.

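### The fifth gated secondary endpoint is named as change from baseline on CGIS, but the only planned test compares the proportion of patients with any decrease

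*SAP*

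**What the plan says.** **Name.** Protocol Section 2.2 lists the fifth secondary endpoint as "Change From Baseline to Month 6 on Change on Clinical Global Impression of Severity (CGIS) (OFF-state"; the Protocol Synopsis (Section 1.0) names it in the same way. SAP Sections 4 and 8.3.8 do likewise, and SAP Section 8.3.1 puts "Change from baseline to Month 6 on CGIS (OFF-state" fifth and last in the fixed testing sequence. For a dose that succeeds on the primary endpoint, "the secondary endpoints for that dose group will be tested in a hierarchical manner at alpha 0.025".

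**Test.** The CGIS paragraph of SAP Section 8.3.8 states: "For CGIS, responders are defined as a decrease in CGIS score from baseline to Month 6". It continues: "CGIS will be analyzed for responders using logistic regression method". Change from baseline at each visit receives descriptive statistics only.

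**General rule.** SAP Section 8.3.3 sets an MMRM "with change from Baseline score as the response (dependent variable) and with Baseline value as a covariate", but only for endpoints treated as continuous. Section 8.3.8 assigns that model by name to the three MDS-UPDRS secondary endpoints and not to CGIS.

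**Declared changes.** SAP Section 8.1 says: "There have been no changes in the planned analyses in the study protocol".

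**The concern.** Position 5 carries one name and a different test. If it is reached and significant, the natural report is an effect on change from baseline in CGIS, yet the p-value would concern the proportion of patients with any decrease.

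The two quantities can diverge. Under the responder rule, a patient who stays at 3 and one who goes from 3 to 6 are both non-responders, so moving patients from worse to unchanged adds nothing to the test statistic. That matters in a degenerative disease. The Protocol Introduction argues for multi-target treatment "if we are to have a good chance of at least halting disease progression", and Protocol Section 4.1 claims a disease-modifying effect for this drug.

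The naming does not look like shorthand. PGIC is called a percentage of responders in the hierarchy and is analysed as one. The MDS-UPDRS endpoints are called changes and are analysed as changes. Only CGIS is named one way and tested another.

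**Working it through.** **1. The plan's own figure.** The documents give no power, rate or effect size for CGIS. The nearest stated figure is for MDS-UPDRS Part II in SAP Section 8.10.2: 174 per arm, difference 3, SD 8, two-sided 0.025, power 90%.

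- Standard error = 8 × √(2/174) = 0.858; ratio = 3/0.858 = 3.498.
- Power = Φ(3.498 − 2.241) = 89.6%. The stated figure reproduces, and with it the alpha convention (critical z = 2.241).

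**2. Inputs for CGIS.**

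- Evaluable patients: 174 × (1 − 0.06) = 163.6, taken as 164 per arm. Both inputs are in SAP Section 8.10.2.
- Alpha: two-sided 0.025 (SAP Section 8.3.1).
- **Assumed** placebo distribution of change (−2/−1/0/+1/+2): 3/17/50/24/6%. So 20% improve and 30% worsen; mean +0.13, variance 0.7531.

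**3. Formulas** (normal approximation, n = 164 per arm).

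- Mean change: power = Φ(d/SE − 2.241), with SE = √[(variance placebo + variance active)/n].
- Responders: the same, with d the difference in proportion with any decrease and SE = √[(p₁(1−p₁) + p₂(1−p₂))/n]. When p₁ = p₂, the two-sided rejection rate is alpha.

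**4. Worked case: worsening prevented only.** Assumed active 3/17/66/12/2%: mean −0.07, variance 0.4851.

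- Change: d = 0.20; SE = √(1.2382/164) = 0.0869; ratio 2.302; power = Φ(0.060) = 52%.
- Responders: 20% in both arms, d = 0; rejection rate 2.5%. Worsening has fallen from 30% to 14%, and the test does not register it.

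**5. All four assumed active distributions.**

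| Active (−2/−1/0/+1/+2, %) | Improve, placebo → active | Worsen, placebo → active | Mean difference | Power, change | Power, responders |
|---|---|---|---|---|---|
| 3/17/66/12/2 | 20 → 20% | 30 → 14% | 0.20 | 52% | 2.5% |
| 4/24/54/15/3 | 20 → 28% | 30 → 18% | 0.24 | 64% | 30% |
| 5/25/50/16/4 | 20 → 30% | 30 → 20% | 0.24 | 60% | 45% |
| 3/32/35/24/6 | 20 → 35% | 30 → 30% | 0.15 | 22% | 80% |

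The third row is symmetric: 10 points more improve and 10 points fewer worsen. The fourth adds improvers and leaves worsening alone, and there the responder test is clearly stronger. A pooled-variance version of that responder test gives 79%.

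**6. Sensitivity to the assumed shape.** With three categories (better/same/worse) and 163 per arm:

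- Six assumed pure-slowing patterns give 21–59% power on mean change. The responder difference is zero in all of them; simulation of two of them (20,000 runs each) gave responder rejection rates of 2.5%.
- Moving the whole distribution by 0.375 SD (3/8, the standardised effect planned for Part II) over five assumed placebo patterns gives 75–79% on change and 46–59% on responders.

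**The case against.** **A responder endpoint may be intended.** The SAP's secondary objective is worded as improvement, Phase 2a is described as improvement over about 25 days, and PGIC is also an improvement-responder endpoint. The sentence on halting progression concerns combination therapy in general. This stands as a defence of the choice of analysis. It does not defend the name: if the proportion is intended, the gated endpoint should be called that.

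**The general MMRM rule might cover CGIS.** Section 8.3.3 applies only to endpoints treated as continuous, and Section 8.3.8 gives CGIS its own rule. The specific rule is the clearer reading.

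**Section 8.1 may not be contradicted.** The protocol gives no CGIS analysis method and defers detailed rules to the SAP. That is fair, so the undeclared responder definition is a minor point.

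**Stronger readings to resist.** A reader might infer that a drug which slows worsening must score zero. That holds only if the effect moves patients from worse to unchanged and adds no decreases. A reader might also infer that the responder test is generally the weaker one; the fourth row of the table shows otherwise. Nor is the endpoint wholly untested: the responder variable is a dichotomy of Month 6 change, and change by visit will still be tabulated.

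**Conclusion.** The mismatch holds on the text: the gated endpoint is named as a change, and its only inferential analysis is a responder proportion. That is wrong as written, whichever endpoint the sponsor intends.

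The effect on power depends on where benefit falls. The loss is total for pure slowing and partial for mixed effects, and it becomes a gain when benefit is confined to extra improvers. Every CGIS distribution used here is an assumption, so these figures show direction and range and do not predict the trial's power.

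The consequence is limited. CGIS is formally tested for a dose only after that dose has won the primary and four earlier secondary endpoints, and nothing is gated behind it. The correction should be made before unblinding, but it does not threaten the primary conclusion.

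**What to change.** **Preferred.** In SAP Section 8.3.8, make the position-5 test a comparison of CGIS change from baseline to Month 6. Use the same MMRM as for the other change endpoints (CGIS is collected at baseline and Months 1, 2, 3 and 6) or an ordinal model. Set code 1, labelled not assessed, to missing before deriving any change. Otherwise a non-assessment is averaged in as the lowest severity, and it counts as a decrease in the responder analysis too. Keep the responder logistic regression as supportive.

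**Alternative.** If the responder proportion is the intended gated endpoint, rename it in Protocol Sections 1.0 and 2.2 and SAP Sections 4, 8.3.1 and 8.3.8, and declare it in SAP Section 8.1. Code 1 still needs to be set to missing.

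**Cost.** The preferred route takes one paragraph of SAP text and one model run before unblinding. Its drawbacks are that an MMRM treats an ordinal scale as continuous, which the ordinal model avoids, and that power is lower if benefit is confined to extra improvers. The alternative costs only wording in two documents, but leaves a gated test that cannot detect pure slowing.
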